Study Protocol

Official Title:

Anhedonia, Development, and Emotions: Phenotyping and Therapeutics (ADEPT)

ClinicalTrials.gov ID (NCT number):

NCT05487885

Protocol Date:

2/19/2025

Scientific Background

Anhedonia—difficulties with reward-focused motivation, anticipation, and effort—predicts poor treatment response and pernicious clinical course in people with depression. A core symptom that also anchors a subtype of depression, anhedonia often precedes the emergence of serious psychopathology, increases risk for suicidality, and reduces the likelihood of responding to pharmacologic or psychosocial treatment (McMakin et al., 2012; Rizvi et al., 2016).

Adolescence to young adulthood is the optimal developmental point for investigating anhedonia in order to improve treatment outcomes. Adolescence is a period of vulnerability for anhedonia, possibly through convergence of changes in frontostriatal reward, dopamine (DA), and reward-related behavioral systems. Anhedonia and depression both begin during adolescence, perhaps not coincidentally during the development of anhedonia's putative neural substrate, the frontostriatal reward system. This neurobehavioral shift, in combination with an early stage in the clinical course of depression, creates an opportunity during adolescence and early adulthood to understand and potentially change the influence

of anhedonia.

The development of anhedonia could reflect diminished DA availability, undermining frontostriatal reward integration and resulting in the persistence of depression or related changes in mood and behavior.

DA can be measured non-invasively by MRI proxy. Brain tissue iron is critical for DA synthesis (Ortega et al., 2007; Zucca et al., 2017), is predominant in the basal ganglia (Haacke et al., 2005), increases through early adulthood (Larsen & Luna, 2018; Peterson et al., 2019), is associated with PET indices of DA availability (Larsen et al., 2020), mediates developmental specialization of frontostriatal functional connectivity through adolescence (Parr et al., 2021), and can be measured non-invasively with MRI. Three indirect indices of DA availability depend on brain tissue iron: R2' is linearly related to striatal tissue iron (Sedlacik et al., 2014), which co-localizes with DA vesicles (Larsen et al., 2020); T2* is a relative measure of tissue iron that can be obtained from fMRI; Neuromelanin (NM) is the pigment that indicates density of nigrostriatal DA neurons (Sulzer et al., 2018; Cassidy et al., 2019).

Inflammation is associated with anhedonia and depression, perhaps particularly in adolescence, and is postulated to exert its influence through changes in striatal dopamine and function in frontostriatal reward circuitry. The relation of inflammation to depression, including in adolescents, is widely documented (Mitchell & Goldstein, 2014), with anhedonia postulated as a specific neuroinflammation-related symptom (Miller & Raison, 2016). Low striatal DA availability and signaling are considered a key mechanism of the inflammation-depression association (Felger & Treadway, 2017). The immune system undergoes considerable development during adolescence (Osugi et al., 1995), with putative consequences for anhedonia (Brenhouse & Schwarz, 2016).

Assessing positive affect, social experiences, sleep, and symptoms in real life and real time provides rich, powerful information on how anhedonia operates in relation to functioning. Beyond the traditional, retrospective, lab-based measures of anhedonia, techniques to measure real-life experiences and behavior using smartphone apps provide greater temporal, featural, and contextual precision that will advance understanding of anhedonia. Social experiences reveal the consequences of anhedonia for functioning, and sleep is critical to affect regulation.

TBS to dmPFC holds promise for reducing anhedonia and improving clinical course in young people with depression. In contrast to the long-duration,

dorsolateral prefrontal cortex-focused TMS approach to depression, we have used TBS—a briefer and more easily tolerated form of TMS—to dmPFC, a target in frontostriatal reward circuitry. Based on our findings and the literature (e.g., Forbes & Dahl, 2012), our guiding hypothesis is that youth with depression exhibit excessive dmPFC response, which serves to dampen VS responding. Thus, our goal is to reduce dmPFC activity through continuous TBS.

PA Training is a psychosocial add-on intervention that could enhance the effects of TBS. PA Therapy (Craske et al., 2016) is an innovative cognitive and experiential technique developed to address anhedonia specifically and, ideally, change altered patterns of frontostriatal function. Standing in contrast to Cognitive Behavioral Therapy, PA training has efficacy for enhancing positive affect and reducing negative affect (Craske et al., 2018). This treatment can be easily applied, and we propose that it will enhance neural circuit-level changes elicited by TBS.

Examining the development of anhedonia can provide critical knowledge about its role in the course and severity of depression, its influence on healthy functioning, and the functional consequences of disrupting its influence with therapeutic approaches involving neuromodulatory, cognitive-behavioral, and pharmacologic techniques. This developmental focus will provide a foundation for optimal treatment assignment, development of more effective treatments, and the opportunity to put young people on a path toward resilience and thriving.

The innovation of the study lies in its strategy for capturing anhedonia, manipulating its mechanisms, and trying to improve the clinical profile of young people who experience it. The features that make it innovative and high-impact include its longitudinal examination of early anhedonia; use of a frontostriatal rather than a dorsolateral PFC target, compressed schedule, and theta burst for TMS; addition of PA Therapy-based cognitive-behavioral exercises to TBS; non-invasive measurement of DA availability; and multi-modal investigation of anhedonia (across neuroimaging, neuromodulation, cutting-edge pharmacotherapy, immunology, ambulatory experience sampling and sensor technology, and sophisticated computational techniques).

Study Objectives

Goal 1. Uncover the complex nature of anhedonia using high dimensional, multi-modal data that captures neural, behavioral, and experiential mechanisms in adolescents and young adults with depression. We will focus on function in neural

reward circuitry using resting and task fMRI; dopamine (DA) availability using MRI; inflammatory markers; ecological momentary assessment (EMA) of mood, social experiences, and symptoms; and sensor technology to assess motor activity, location (e.g., proportion of time spent at home), sleep/wake patterns, and social context (e.g., isolation). Machine learning techniques will compute digital phenotyping, cross-method computational phenotyping, and clustering profiles. The hypothesis is that anhedonic depression is characterized by disrupted frontostriatal function, low dopamine availability, altered inflammatory markers, low activity level, and social isolation. In addition, phenotypes based on this combination of methods will be detectable.

Goal 2. Manipulate the neural mechanisms of anhedonia using 3 treatments found to improve anhedonia, putatively through influence on frontostriatal function. These are (1) continuous theta burst stimulation (cTBS), a form of transcranial magnetic stimulation, to dorsomedial prefrontal cortex (dmPFC); (2) positive affect (PA) exercises drawn from a psychosocial treatment shown to improve PA and treat depression. All participants will receive a 20-session (2/day), 2-week course of cTBS targeting frontostriatal reward circuitry. With a brain target related to anhedonia, more dense schedule, and briefer administration than standard transcranial magnetic stimulation (TMS) for depression, we will attempt to improve anhedonia and depression by reducing (1) high dmPFC function, which we have found is associated with adolescent anhedonia (Healey et al., 2014) and (2) dmPFC dampening of ventral striatal (VS) response. Participants who receive TBS will receive PA exercises drawn from PA Therapy (Craske et al.). Outcomes will include anhedonia phenotypes computed in Goal 1, as well as traditional clinical variables and brain function.

Goal 3. Conduct sophisticated analytics to examine the association of computational phenotypes of anhedonia with device/pharmacologic response, clinical course, and functioning over 1 year. To connect the descriptive analytics of Goal 1 with treatment response (Goal 2), development, and clinical course, we will use machine learning techniques with our high-dimensional, integrative, multi-modal data to examine predictors of response to TBS and the relation of biological, digital, and clinical factors in the persistence of anhedonia and its phenotypes. We will also be able to test other questions, including within-person pathways to healthy functioning; prescriptive analytics to consider how to assign to TMS; change point analyses for fluctuation in anhedonia after treatment; and contributions to worsening or improvement of anhedonia over 1 year.

Study Design & Methods

The study has a longitudinal design in which participants complete 2 sets of activities:

Phase 1: Phenotyping. This includes assessment with diagnostic interview, questionnaires, behavioral tasks, MRI, app-based digital assessment, and blood draw for inflammatory markers. These activities will occur at 4 time points over the course of 1 year/participant (study entry, approximately 4 months, approximately 5 months, and approximately 1 year), and all participants will complete them.

Phase 2: Therapeutic activities: 20 theta burst stimulation (TBS) sessions for all participants and 10 sessions of either positive affect (PA) training or control training.

This design allows the phenotyping and description of anhedonic depression; the prediction of response to treatment; the computation of prescriptive treatment assignment retrospectively; and the detection of changes in phenotype and component characteristics (e.g., functional connectivity of reward circuitry) in relation to treatment, development, and time. Ultimately, the knowledge gained will inform the prevention and treatment of anhedonic depression by taking a clinical neuroscience approach to understanding this condition, its mechanisms, and its improvement with treatment.

The primary endpoints are anhedonia severity and depressive disorder. The secondary endpoints include frontostriatal circuit function, DA availability, peripheral inflammation, reward behavior, subjective positive affect, locomotion and motor activity, sleep characteristics, and phenotype severity/group.

The ADEPT Study will be divided into 2 Phases, with phenotyping in Phase 1 and therapeutics in Phase 2. Phase 1 includes MRI, blood draw for inflammatory markers, behavior tasks, diagnostic interviews, questionnaires, and phone-based EMA and sensor data collection activities. Phase 2 includes TBS and PA training. All participants will complete both phases.

1. Eligibility - both Phases:

At the eligibility visit for Phase 1, participants will complete written informed consent; the SCID-5 to diagnose DSM-5 disorders; the MADRS to assess depression severity; the SHAPS to assess anhedonia; a medical history form; and a treatment

history form. The eligibility visit may be broken into two or three parts as needed, and some procedures may be conducted virtually as appropriate.

For Phase 2, participants will complete self-report measures of health relevant to TMS, a urine drug screen, and a urine pregnancy test (for those assigned female at birth). For Phase 2 participants, the visit to the M-CTRC lab at the time point after TMS will include vital signs, urine drug screen, urine pregnancy screen, and ECG. The PI or proxy (i.e., co-investigator or study physician) will review materials for eligibility and sign to confirm. Medical findings will be reviewed by a board-certified physician co-investigator prior to the TMS procedures.

Once informed consent for phase 2 has been completed, a consult with a study physician will occur, in which the physician will determine whether TMS treatment would be appropriate for the participant. If TMS is not deemed appropriate, the participant will not continue in the study.

Eligibility procedures may be ended early if it is clear that a participant does not meet inclusion/exclusion criteria (eg., participant reports taking an exclusionary medication).

2. Interview and Questionnaires - Phase 1:

Participants will complete SCID diagnostic interviews at study entry. Also at study entry, the affect induction tasks will be completed (5-10 minutes) which involves a conversation with the participant and comparing vocal data. Participants will complete the MADRS interview on depressive severity and the SHAPS questionnaire on anhedonia severity at study entry, pre/post-TMS, and at 1 year. Interviews may be conducted in person or by HIPAA-compliant zoom virtual format.

At 4 time points, participants will complete other self-report questionnaires. These time points are at entry, and approximately at month 2-4 (after TBS), month 4-6, and 1 year. Questionnaires assess symptoms, demographic characteristics, and relevant experiences (e.g., trauma history).

3. MRI - Phase 1:

At the first 2 time points above, participants will complete a 1.5-hour (scan 1-2) or a 1-hour scan (scan 3) at the CMU Bridge Center or Presby MRRC. The MRI visits will involve 2 resting state MRI scans, a guessing reward fMRI task in which participants can win money, scans to assess striatal tissue iron and midbrain neuromelanin, and a structural scan. Scans 1-2 will also include an fMRI task

involving effort to obtain reward, if participant interest and time limits allow. The tissue iron and neuromelanin scans will be used to compute proxy variables for dopamine availability, allowing measurement of dopamine function in reward circuitry. Participants can expect these visits to take approximately 1.5 hours (2.25 hours if effort task is included).

4. Inflammatory Markers - Phase 1:

At the first 2 time points (described above), participants will complete a 30mL blood draw. Venipuncture will be conducted by a phlebotomist at the WPH phlebotomy lab. The venipuncture procedure will be billed to study accounts and not to participants or their insurance.

5. Behavior - Phase 1:

At the first two time points as above, participants will complete behavior tasks that are presented by computer and assess reward processing.

6. Digital phenotyping - Phase 1:

For approximately the first 6 and last 3 months of participation in the study, participants will complete an ecological momentary assessment (EMA) procedure with collection of self-reported mood, symptoms, and related experiences (e.g., sleep quality) for 7-day bursts, with one burst per month. EMA will occur by phone, using app, such as EARS or WDX, text, or browser, to present surveys and collect data. Data will be encrypted, protected, and stored using HIPAA-compliant techniques.

For the entire year of participation in the study, the EARS app may collect data from phone sensors to determine variables related to anhedonia, such as motor activity (from accelerometer) and location (from GPS). Data will be encrypted, protected, and stored using HIPAA-compliant techniques.

7. Computer Cognitive Tasks:

After the first and second Phenotyping Visits, participants will complete computer tasks remotely (approx. 1 hour). They will receive a link by email and will complete the tasks when convenient for them. The tasks will include an effort-based reward task in which participants make decisions about pressing a button to obtain small or large rewards and a task in which participants go through learning and unlearning using aversive stimuli (a scream sound). A questionnaire will be in the middle of the two tasks. This questionnaire serves as a break to separate the acquisition and extinction phases, which is important for the task to be realistic and valid, and data will not be collected from the questionnaire.

8. Theta Burst Stimulation (TBS) - Phase 2:

Participants in Phase II of the study will undergo 2 sessions of continuous TBS (cTBS) per day over 10 days (on weekdays, over 2 weeks; 20 sessions total). TBS is a form of TMS. TBS will be conducted by research personnel who have undergone comprehensive training according to the SOP previously provided to the IRB for STUDY20050081.

TBS will be administered with the MagPro X100 Transcranial Magnetic Stimulation (TMS) system, which is FDA cleared for Theta Burst Stimulation (TBS) treatment of Major Depressive Disorder in adult patients who have failed to receive satisfactory improvement from prior antidepressant medication in the current episode (k170114, k150641, and k171481). Thus, the device is acceptable for use in this research context.

The total time of each pair of sessions will be approximately 1 hour, with each administration of TBS lasting approximately 2 minutes. Before the first TBS session on each TBS session day (i.e., 10x during the study), participants will be asked "How well did you sleep last night?" Additionally on each TBS session day, participants will complete self-report forms on recent substance use and medical status. If drug use or change in medical status is reported, a team member will assess for such change and contact a study MD as needed (e.g., participant has started a new medication) to determine whether the participant can continue to receive TBS. At the beginning and end of each TBS visit (once for every pair of TBS sessions, or 10x total), participants will rate their pain levels. After all TBS sessions have been completed, participants will complete an acceptability scale. Participants can miss up to two consecutive days of TMS as long as they come for the appropriate total number of visits.

9. PA training - Phase 2:

At each TBS visit, participants in Phase II will complete a positive affect (PA) training task (30-45 min per training session). The exercises in the PA training are designed to enhance reward processing and PA, and they will be adapted from Positive Affect Therapy, a psychosocial treatment targeting anhedonia and intended to improve disrupted frontostriatal function (Craske et al., 2016). This treatment reduces negative affect and enhances PA (Craske et al., 2018). PA training will be administered by trained research staff.

10. Follow-up assessment - Phase 1:

The follow-up assessment approximately 1 year after entering the study will include

the MADRS and questionnaires described above. The participant will also complete the study completion survey.

Eligibility Criteria

Inclusion criteria are as follows:

Phase 1 (all participants)

- Age 15-25
- Current DSM-5 depressive disorder
- Severity ≥ 12 on MADRS
- Moderate-severe anhedonia (75% of sample) or low anhedonia (25% of sample)

Phase 2 (for participants in TBS phase, in addition to above)

- ≥ 1 failed antidepressant trial (for qualification for Phase 2 of study and definition of non-response to TMS to be eligible for ketamine) = Treatment for at least 6 weeks with an antidepressant medication reaching recommended dosage for adults for at least 3 weeks of the treatment (e.g., 20 mg fluoxetine)

Exclusion criteria are as follows:

Phase 1 (all participants)

- Lifetime psychosis, bipolar disorder, autism spectrum disorder, or developmental disorder
- Serious, unstable neurological disorder (e.g., seizure disorder)
- Brain injury with loss of consciousness
- Moderate-severe substance use disorder, past 6 mos.
- MRI contraindications (e.g., claustrophobia or ferromagnetic objects that cannot be removed from the body, weight > 300 lbs)

Phase 2 (for participants in TBS phase, in addition to above)

- Serious, unstable respiratory or cardiovascular illness
- Pre-TBS: Alcohol binge in past week, which is defined as the number of drinks over a two-hour period greater than or equal to: 4 drinks for women, 5 drinks for men, 3 drinks for girls (15-21) and 4 drinks for boys (ages 15-21).
- Pre-TBS: Current illicit stimulant use
- Pregnancy
- High blood pressure
- Lifetime recreational ketamine or PCP use
- Lifetime history of seizure

Statistical Considerations

Analyses will test pre-/post-treatment change in severity of depression symptoms (from MADRS) and anhedonia symptoms (from SHAPS) using repeated measures tests. Change in symptoms will be computed in separate models for TMS+PAT and for TMS+PAT, then ketamine, and for depression and anhedonia. Given the small number of tests, there will not be additional correction for Type I error, and statistical threshold for each test will be set at $p < .05$. For statistical power, G*Power 3.1 tests indicate that for repeated measures models with the original target sample of 100 participants, we will have >95% power to detect change in symptoms with medium effect size of $f=.0.2$.

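### Goal 3 offers prescriptive analytics for assigning people to TMS, but everyone receives cTBS with no concurrent comparator, so these data cannot identify who benefits from TMS versus no TMS

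*Combined protocol and SAP*

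**What the plan says.** Study Objectives, Goal 3, lists further questions the study will be able to test, one of which is "prescriptive analytics to consider how to assign to TMS". Study Design & Methods then says that the design allows "the computation of prescriptive treatment assignment retrospectively"; that sentence does not name a treatment.

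On who receives TMS, the document says:

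- Goal 2: "All participants will receive a 20-session (2/day), 2-week course of cTBS targeting frontostriatal reward circuitry".
- Study Design & Methods, Phase 2: "20 theta burst stimulation (TBS) sessions for all participants and 10 sessions of either positive affect (PA) training or control training".
- Study Design & Methods, overview of the two phases: "All participants will complete both phases".
- Item 1, Eligibility: "If TMS is not deemed appropriate, the participant will not continue in the study".

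No sham, waitlist, delayed-start or external comparator is described. Statistical Considerations covers only pre/post change in MADRS and SHAPS. It gives no estimand, comparator or method for a prescriptive analysis.

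**The concern.** Assigning a treatment by patient features means comparing two expected outcomes for the same kind of person, one with the treatment and one without. This plan observes only the first. A feature that goes with large improvement after cTBS may mark people who would have improved anyway, people whose entry scores were high partly by chance (entry requires MADRS of at least 12, so some regression to the mean is expected), or people whom cTBS truly helps more. Predicted response mixes all three, and the design cannot separate them.

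At stake is a stated capability of the study. If predicted response under cTBS were used to decide who should get TMS, the rule could favour people who gain nothing extra, or those who gain least. More participants or more flexible machine learning would not help, because the missing quantity is never observed.

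**Working it through.** **The plan's only figure.** Statistical Considerations states more than 95% power for pre/post change with 100 participants and f = 0.2 (the printed value has a stray decimal point). For a within-person F test, λ = f²·N·m/(1 − ρ). Assuming one group, m = 2 measurements and ρ = 0.5, none of which the document states, λ = 0.04 × 100 × 2 / 0.5 = 16, and with 1 and 99 degrees of freedom at α = 0.05 the power is 97.7%. For m = 2 it runs from 80.0% at ρ = 0 through 91.7% (0.3) and 95.1% (0.4) to 99.9% (0.7). The figure is reproducible for ρ of about 0.4 or more. It concerns pre/post change and says nothing about an assignment rule.

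**What an assignment rule needs.** Let X be a standardised baseline feature, Y1 the improvement with TMS and Y0 the improvement over the same period without it:

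- E[Y1 | X] = a1 + b1·X
- E[Y0 | X] = a0 + b0·X
- Benefit: E[Y1 − Y0 | X] = (a1 − a0) + (b1 − b0)·X

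The rule depends on b1 − b0. With everyone on cTBS, the data estimate a1 and b1. The number of participants with a concurrent Y0 is zero by design, whatever the enrolment, so a0 and b0 receive no information.

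**Illustration (assumed values, not from the document).** Take a1 = 0.5, b1 = 0.5, a0 = 0 and X standard normal. The mean of X in its upper half is √(2/π) = 0.798, and in its lower half −0.798. Mean benefit in each half is 0.5 ± (0.5 − b0) × 0.798.

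| Slope without TMS, b0 | Observed slope under TMS | Slope on TMS benefit | Benefit, high-X half | Benefit, low-X half |
|---|---|---|---|---|
| 0.5 | 0.50 | 0.00 | 0.50 | 0.50 |
| 0.0 | 0.50 | +0.50 | 0.90 | 0.10 |
| 0.8 | 0.50 | −0.30 | 0.26 | 0.74 |

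The observable data are the same in all three rows. In the first, X is purely prognostic. In the third, giving TMS to predicted responders selects those who gain least.

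**Could other data in the plan supply Y0?**

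- *Pre-TBS measurements.* Item 2 schedules MADRS and SHAPS at entry and again before TMS, and item 6 has monthly EMA bursts over about the first six months, some of which may precede TBS. These are off-TMS data, but from an earlier period, soon after selection on severity. Using them as each person's no-TMS course over the treatment period needs extrapolation assumptions that the plan does not state and the data cannot test.
- *A Phase 1-only group.* Eligibility Criteria uses the wording "Phase 2 (for participants in TBS phase, in addition to above", which hints at one, in conflict with the statement that everyone completes both phases. Such a group could differ by the Phase 2 requirement of a failed antidepressant trial. To the extent that this rule separates the groups, there is no overlap on it. No such comparison is planned.
- *People unsuitable for TMS.* They leave the study, so they provide no follow-up.

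**Is PA versus control training available?** It is the only between-person treatment contrast named, and it appears only in the Phase 2 sentence of Study Design & Methods. Goal 2, the overview of the phases and item 9 describe PA training with no control option. Statistical Considerations names models for TMS with PA training, and for that followed by ketamine, with no control-training model. No allocation ratio or randomisation is stated.

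**The case against.** The strongest reply is that this is one clause in an exploratory list. It is absent from the primary and secondary endpoints and from Statistical Considerations, and no planned test, sample size or procedure depends on it. That stands as a limit on its weight. It does not remove the point, because exploratory status does not make an unidentified quantity estimable, and the document presents the analysis as something the study will be able to test.

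A reader might also infer three stronger things that the documents do not support:

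- *That the study will report prognosis as evidence of who should get TMS.* This is a forecast. The document gives no method or reporting plan for the analysis and states no such conclusion.
- *That there are no off-TMS outcomes at all.* Symptom scores, and possibly EMA data, are collected before TBS. What is absent is a concurrent no-TMS outcome.
- *That the general design sentence on retrospective prescriptive assignment is wrong and should be deleted.* It does not name TMS and follows directly after the sentence naming PA and control training, so it may refer to that contrast. It needs clarifying.

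Predicting outcome under cTBS remains a legitimate aim and is not criticised here.

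**Conclusion.** The point holds for the TMS clause in Goal 3. How the effect of TMS versus no TMS varies with baseline features is not identified from these data at any sample size without untestable assumptions. This rests on the document's own statements that all participants receive cTBS and complete both phases, and on the absence of any described sham, concurrent untreated or external comparator. The numerical illustration uses assumed values and shows only that benefit could be nil, positive or reversed for the same observed data.

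The consequence is confined to what Goal 3 may conclude. The pre/post analyses and their power statement do not change. It is worth correcting because a stated capability is one the design lacks, and the correction is nearly free. Whether an assignment rule for PA versus control training can be estimated is open: it depends on whether that control arm exists and is randomised, which the document does not settle. Even then, the rule would concern training added to cTBS and would not inform the choice of TMS itself.

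**What to change.** 1. In Goal 3, replace the clause on assigning to TMS with prediction of outcome under cTBS, and state that these models do not support conclusions about who should be assigned to TMS. Alternatively, name an external comparator and the assumptions it requires.
2. In Study Design & Methods, state that the sentence on retrospective prescriptive assignment does not cover TMS versus no TMS.
3. Reconcile Goal 2, Study Design & Methods (including the overview of the phases), item 9 and Statistical Considerations on whether a control-training arm exists and whether allocation to it is randomised. Reconcile the Phase 2 wording in Eligibility Criteria with the statement that all participants complete both phases.
4. If a randomised control-training arm is confirmed, limit prescriptive modelling to PA versus control training, specified as treatment-by-baseline-feature interactions. Predictors may include anything measured before TBS starts, such as pre-TMS MADRS and SHAPS and any pre-TBS EMA, and need not be restricted to study entry. If the arm is not confirmed, drop the prescriptive claim altogether.

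The cost is edited wording and a narrower exploratory claim. No new data are needed.

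### No PA-versus-control comparison is planned, the document contradicts itself on whether a control-training group exists, and the pre/post tests cannot show that PA training adds to TBS

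*Combined protocol and SAP*

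**What the plan says.** **Analysis.** Statistical Considerations is the only statistics section. It states: "Analyses will test pre-/post-treatment change in severity of depression symptoms (from MADRS) and anhedonia symptoms (from SHAPS) using repeated measures tests". Separate models are named for TMS+PAT and for TMS+PAT followed by ketamine, each for depression and for anhedonia, at p < .05 per test. The power statement (above 95%, 100 participants, f printed as .0.2) refers to change in symptoms only.

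**Who gets what in Phase 2.** The text is not consistent:
- Study Design & Methods, Phase 2: "20 theta burst stimulation (TBS) sessions for all participants and 10 sessions of either positive affect (PA) training or control training".
- Study Objectives, Goal 2: "Participants who receive TBS will receive PA exercises drawn from PA Therapy".
- Study Design & Methods, phase summary: "Phase 2 includes TBS and PA training. All participants will complete both phases".
- Item 9, PA training - Phase 2: "At each TBS visit, participants in Phase II will complete a positive affect (PA) training task".

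Control training appears only in the first of these. Nowhere is there a method of allocation, an allocation ratio or a description of the control training.

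**TBS.** Goal 2 states: "All participants will receive a 20-session (2/day), 2-week course of cTBS targeting frontostriatal reward circuitry". There is no sham or untreated group.

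**The add-on hypothesis.** The Scientific Background says of PA training: "we propose that it will enhance neural circuit-level changes elicited by TBS".

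**The concern.** A hypothesis that one treatment adds to another needs a comparison between people who had the addition and people who did not. The plan has none. If some participants receive control training, they belong to no named model, and the comparison that would justify having them is missing. If nobody does, the study has a single treated group and cannot address the add-on hypothesis.

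In both cases the planned tests measure how far scores move from before to after treatment in people enrolled while depressed. Such movement combines any effect of TBS and PA training with natural course, expectancy and staff contact. A small p-value would show that scores changed, not why. Anhedonia severity and depressive disorder are the primary endpoints, so this limits the trial's main clinical conclusion.

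**Working it through.** **1. The plan's own power figure.** Inputs from Statistical Considerations: N = 100, alpha = 0.05, f read as 0.2. Assumed, because not given: m = 2 time points, correlation ρ = 0.5, a within-person F test.

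- λ = f² × N × m / (1 − ρ) = 0.04 × 100 × 2 / 0.5 = 16, with 1 and 99 degrees of freedom.
- Power = 97.7%, consistent with the stated figure of above 95%.
- With m = 2, power is 80.0% at ρ = 0, 91.7% at ρ = 0.3 and 99.9% at ρ = 0.7, so the figure depends on a correlation that the plan does not state.
- Reading f as 0.02 gives about 7%, so 0.2 must be meant.

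With two time points, f = 0.2 is a pre/post change of 2 × 0.2 = 0.4 SD. The stated power is sound for that test and covers nothing else.

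**2. What the pre/post test does when treatment has no effect.** Let d be background improvement in SDs of the change score. The values of d are illustrative; the documents give none. For a paired t test the non-centrality is d × √n.

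| d | non-centrality, n = 100 | P(p < .05), n = 100 | P(p < .05), n = 50 |
|---|---|---|---|
| 0 | 0 | 5% | 5% |
| 0.2 | 0.2 × 10 = 2.0 | 51% | 28% |
| 0.3 | 3.0 | 84% | 55% |
| 0.4 | 4.0 | 98% | 79% |

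**3. What a between-group comparison could detect.** Assumed: 100 participants split 50:50, no dropout, two-sided 0.05, difference d in SDs of the change score. Non-centrality = d × √(50/2) = 5d, with 98 degrees of freedom.

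| d | 5d | Power |
|---|---|---|
| 0.2 | 1.0 | 17% |
| 0.3 | 1.5 | 32% |
| 0.4 | 2.0 | 51% |
| 0.5 | 2.5 | 70% |

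- 80% power is reached at d = 0.566, about 0.57. The normal approximation agrees: (1.960 + 0.842) × √(2/50) = 0.56.
- Baseline adjustment helps. At a pre/post correlation of 0.5, where the raw and change-score SDs are equal, the detectable difference falls to 0.566 × √(1 − 0.5²) = 0.49 SD.
- By the normal approximation, d = 0.4 on change scores needs about 99 per group for 80% power and 163 per group for 95%.

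At ρ = 0.5, the 0.4 SD that the plan detects with 97.7% power as a within-person change has 51% power as a difference between groups.

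**The case against.** **The control group may not exist.** A reader might infer that the trial runs two arms and discards one at analysis. The documents do not establish that. Control training is mentioned once, against three descriptions without it and models for TMS+PAT only. Other text also fits the described procedures poorly: Goal 2 announces three treatments and lists two, and ketamine appears in the eligibility criteria and the models without any described procedure. The control-training phrase may be of the same kind. This objection stands, and it is why reconciliation comes first. It does not rescue the analysis, because without a control group the add-on hypothesis cannot be tested at all.

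**Regression to the mean.** A reader might infer that selection on MADRS ≥ 12 by itself produces a spurious pre/post drop. That requires the entry score to serve as the pre score. Item 2 (Interview and Questionnaires) lists a pre-TMS assessment separately from study entry. With equal correlations between visits, the entry cut-off then creates no expected change from pre to post. No figure for it is used here.

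**The hypothesis as worded.** The quoted sentence concerns neural circuit-level change, not MADRS or SHAPS, although the same paragraph also says more broadly that PA training could enhance the effects of TBS. No PA-versus-control test is specified for either kind of outcome. It would be too strong to say that the question can never be tested, since Goal 3 leaves room for exploratory work.

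**The design is open about having no sham, and a test of change is meant to detect change.** Both are true. The rejection rates in step 2 rest on chosen drift values; they show what a significant result cannot establish, not how large the drift will be.

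**Conclusion.** The point holds in this form: no PA-versus-control contrast is specified, the sections disagree on whether a control-training group exists, and the planned tests measure uncontrolled change. This follows from the text and needs no assumption.

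The sizes do rest on assumptions. With no treatment effect and 0.2 SD of background improvement, the planned test is significant about 51% of the time at n = 100. A between-group test with 50 per group needs about 0.57 SD of the change score for 80% power; the documents give no group sizes, allocation ratio or dropout. The sample of 100 is itself described as the original target.

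A reader might also infer that a between-group test would hold its error rate at 5%. That is so only if allocation was random, which the documents never say.

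**What to change.** **First**, reconcile Goal 2, the Phase 2 description, the phase summary, item 9 and Statistical Considerations on whether a control-training group exists.

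**If it does:**
- State how participants were allocated.
- For MADRS and for SHAPS, add a comparison of PA minus control training in all Phase 2 participants as assigned, by ANCOVA or a mixed model adjusted for the pre-TMS score.
- Interpret the difference causally only if allocation was random.
- Report the pooled pre/post change as uncontrolled.
- State that the power above 95% applies to within-person change only, and give the difference detectable between groups at the actual group sizes.

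**If it does not:** remove control training from the Phase 2 description, limit conclusions to uncontrolled change after combined TBS and PA training, and make no claim that PA training enhances TBS.

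**Cost.** Changes to the text and one added model per outcome. No new assessments are needed, because MADRS and SHAPS are already collected before and after TMS. The downside is that the between-group test has less power than the pre/post test, so a modest benefit of PA training could be missed.
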